## **6.3 CT perfusion at selected centres before randomisation (substudy)**

Some centres routinely use CT perfusion in patients with wake-up stroke, and these centres will be invited to participate in a substudy of CT perfusion. All CT scans taken in the trial will be sent to the Trial Co-ordinating Centre for central, blinded analysis.

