## **6.4 Routine use of MRI before randomisation**

Some centres routinely use MRI perfusion or MRI DWI/FLAIR in patients with wake-up stroke. These examinations are not part of the trial, but MRI examinations done of patients included into the trial shall be sent to the Trial Coordinating Centre for central, blinded analysis. Extra brain scanning (CT perfusion or MRI) must not delay treatment, and we will discourage extra scanning if randomisation is delayed more than 20 minutes.

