### **8.3 Best standard care and other treatments**

Both arms will receive best standard care, including intra-arterial interventions for proximal cerebral artery occlusion. If the patient is given tenecteplase, then aspirin or other antiplatelet or anticoagulant drugs shall not be given until 24 hours after termination of infusion and after the control CT brain scan. If the patient was allocated to control, he/she will receive aspirin 300 mg as a loading dose as soon as possible after randomisation. After the first 24 hours the recommended daily dose of aspirin is 75 mg once daily in both the tenecteplase group and the control group. Best standard care during the first week also includes treatments to maintain normal homeostasis (temperature, blood glucose, hydration, nutrition), as well as lipid lowering and blood pressure lowering drugs, in accordance with clinical guidelines. Clinical examinations, including additional CT scans will be performed as clinically indicated.

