**Table 2. Scheme for visits and examinations**

	Days			Months
	1	2	7	3
Clinical visit	x		x	
Routine blood analysis	x		x	
CT + CT angiography (if possible) before randomisation	x			
CT perfusion, at selected centres	(x)			
CT + CT angiography (if possible) 24±6 hrs after randomisation		x		
Centralised follow-up				x

Day 1 is the day of entry into the trial. \*Day 7 or day of discharge, whichever occurs first.

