### 9.1 Visits and examinations during stay in hospital

Clinical visits: These will be performed on day 1 (at baseline) and day 7 (or on the day of discharge, whichever occurs first). NIHSS will be performed at both times. ECG will be performed on day 1. Clinical events will be recorded on day 7 (or on the day of discharge). Outcome assessors will be blinded to the assigned treatment group.

Routine blood analysis will be performed on day 1 (at baseline) and day 7 (or on the day of discharge, whichever occurs first). Tests on day 1 will include: haemoglobin, creatinine, blood glucose, platelets, prothrombin time/INR, aPTT, TT and/or eucarin clotting time if it is suspected that the patient is taking direct thrombin inhibitors or direct factor Xa inhibitors.

Non-contrast CT and CT angiography (if possible): All patients will undergo non-contrast CT and CT angiography (if possible) before randomisation, and again at 24±6 hours after randomisation. CT angiography at 24±6 hours will only be performed in patients with a positive finding on CT angiography before randomisation.

CT perfusion will be performed at selected centres.

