## 11.2 Statistical analyses

A detailed Statistical Analysis Plan has been drawn up and will be published before breaking the randomisation code. We will analyse the data according to the intention-to-treat principle. Functional outcome will be primarily compared between the study groups by means of ordinal logistic regression, after adjustment for covariates. In a secondary analysis, functional outcome will be dichotomised (mRS score 0-1 vs. 2-6) and analysed by means of logistic regression.

For clinical events we will estimate odds ratios and 95% confidence intervals using logistic regression and estimate hazard ratios and 95% confidence intervals using the Cox proportional hazards model, as appropriate. Interactions will be tested using likelihood ratio tests. The risks of clinical events will be compared using Kaplan-Meier survival analyses and log-rank tests. All analyses will use 5% two-sided level of significance.

We will perform prespecified subgroup analyses of patients with findings suggestive of penumbra (on CT perfusion), of patients included based on presence or absence of DWI/FLAIR mismatch on MRI, of patients with proximal cerebral artery occlusion, and of patients with different time intervals since awakening, controlling for imbalances in baseline characteristics. Subgroup analyses will be prespecified in the Statistical Analysis Plan. Patients treated with intra-arterial intervention for proximal cerebral artery occlusion will also be analysed separately, and the primary effect variable for this analysis will be cerebral arterial patency before intra-arterial intervention.

Any missing components of the baseline NIHSS will be imputed using a regression-based technique, using age and all other components of the NIHSS. A worst-case approach will be used when handling incomplete dates and times for adverse events. For example, events will be assumed to be treatment emergent unless it is clear even from the partial date/time that this is not the case.

As subgroup analyses are of an exploratory nature, no adjustment for multiple comparisons will be made.

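### The protocol names no source image, scale or blinded reader for arterial patency before intra-arterial intervention, the primary effect variable of the separate intra-arterial analysis

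*Protocol*

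**What the plan says.** Section 8.3 of the Protocol allows the procedure in both groups: "Both arms will receive best standard care, including intra-arterial interventions for proximal cerebral artery occlusion". Section 11.2 then plans an analysis of its own for these patients: "Patients treated with intra-arterial intervention for proximal cerebral artery occlusion will also be analysed separately". The outcome is fixed in the same sentence, where the plan states that "the primary effect variable for this analysis will be cerebral arterial patency before intra-arterial intervention".

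Section 9 presents Table 2 as the overview of every visit and examination in the trial. Its vascular imaging entries are "CT + CT angiography (if possible) before randomisation" and "CT + CT angiography (if possible) 24±6 hrs after randomisation". Section 9.1 narrows the second: "CT angiography at 24±6 hours will only be performed in patients with a positive finding on CT angiography before randomisation".

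On reading, section 6.3 says "All CT scans taken in the trial will be sent to the Trial Co-ordinating Centre for central, blinded analysis", and section 6.4 says "MRI examinations done of patients included into the trial shall be sent to the Trial Coordinating Centre for central, blinded analysis".

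Section 10.2 does not list pre-procedure patency. It leaves radiological outcomes to a separate imaging protocol. The earlier protocol version, filed as the Combined protocol and SAP, has the same analysis sentence in its section 11.2 and the same two imaging times. Neither document mentions catheter angiography.

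**The concern.** The analysis asks whether tenecteplase opens the artery before the interventionist does. Answering it takes an image from a narrow window, after randomisation (and after the bolus in the tenecteplase group) and before the procedure, obtained and read the same way in both groups. The main protocol names the variable but gives no image, collection route, patency scale, reader, blinding rule or rule for missing images.

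This is more than a matter of wording. A statistical analysis plan can define a scale late, but analysts cannot supply images that sites were never asked to send. Treatment is open-label, so a patency reading made locally could be made with knowledge of the allocation, and judging partial patency leaves room for opinion.

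The population adds a second difficulty. Membership depends on having received the intervention. A patient whose artery is found open at angiography may not go on to be treated, and would then leave the analysis because of the very outcome it is meant to count.

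**Working it through.** No arithmetic in the plan bears on this point. No sample size, expected patency rate or expected number of intra-arterial procedures is given for this analysis. The target of 600 in section 11.1 belongs to the mRS analysis and does not enter here. The check is therefore a comparison of the plan's images with the window that the variable needs.

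**Step 1: timing.** The 24±6 hour window runs from 24 − 6 = 18 to 24 + 6 = 30 hours after randomisation.

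| Image | Source in Protocol | Relative to drug | Relative to procedure | Can it show the variable? |
|---|---|---|---|---|
| CT angiography, if possible | Table 2, 9.1 | before | before | No, it precedes allocation |
| CT perfusion, selected centres | 6.3 | before | before | No, same reason |
| MRI, where a centre uses it | 6.4 | before | before | No, same reason |
| CT angiography, if possible, 18 to 30 hours, only if the first was positive | Table 2, 9.1 | after | not tied to it; expected to follow it | No |
| Additional CT on clinical grounds | 8.3 | not fixed | not fixed | Only where one happens to include the vessels and fall in the window |

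No scheduled image falls between drug and procedure. Unscheduled CT may do so in some patients, but it is not systematic capture of an endpoint.

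**Step 2: reading.** Central blinded reading is stated for CT (6.3) and MRI (6.4). The blinding of outcome assessors in section 9.1 stands under clinical visits. Section 9.2 concerns the three-month contact, and section 12.6 concerns adjudication of events. None of these assigns a blinded reader to a patency reading at angiography.

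**Step 3: population.** Let p be the share of arteries open at the first angiographic run among patients taken to angiography, and s the share of open arteries that then receive no intervention. Suppose every closed artery is treated. Among treated patients, patency is

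p(1 − s) / [p(1 − s) + (1 − p)] = p(1 − s) / (1 − ps).

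At s = 0 this is p, the quantity wanted. At s = 1 it is 0 in both groups, whatever the drug does. The documents give neither p nor s, so where the trial would lie between these limits cannot be said. The formula shows only that conditioning on treatment removes reopened arteries.

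**The case against.** The strongest reply is that arterial patency is a radiological outcome, and section 10.2 sends radiological outcomes to a separate imaging protocol. Section 11.2 adds that a detailed statistical analysis plan has been drawn up, and the contents list an Imaging Scientific Committee. Neither that imaging protocol nor that plan was available here. Naming a variable in one document and defining its measurement in another is no contradiction. Nor would one expect Table 2, a schedule for patients in general, to list an angiogram obtained in a subset as part of standard care. This stands in part: the documents are silent, and silence is not evidence that nothing is arranged.

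For that reason several stronger readings, which a reader might infer, are not supported:

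- *Catheter angiograms are not collected or centrally read.* No section says so; the imaging protocol may provide for it.
- *The operator's note is the only remaining source.* Operator notes appear nowhere. A repeat CT angiogram taken before the procedure, where one exists, would go to central reading under section 6.3.
- *The analysis cannot be run.* A diagnostic run at the start of the procedure would show the variable and could be retrieved if archived. What is missing is a written route to it.
- *The 24-hour scan would be used and would dilute the difference between groups.* Section 11.2 specifies patency before the intervention, which rules that scan out. Any dilution figure would describe a substitution that the plan does not propose, with reopening rates that it does not give.

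It is also fair to say that the analysis sits beside subgroup analyses that the plan treats as exploratory. That limits the weight of the point. It does not remove it, because the plan itself gives this variable primary status within the analysis.

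**Conclusion.** The point holds as a gap in the main protocol. A named primary effect variable has no stated source image, scale, reader or missing-data rule, and none of the scheduled images falls in the window it requires. The restriction to treated patients is a further weakness, because it leaves out arteries found open and not treated.

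Its reach is limited. It concerns one separate, exploratory analysis; the primary mRS comparison, the sample size and the safety analyses are unaffected. No numerical size can be given from the documents.

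The conclusion rests on two assumptions: that the variable is meant to show a treatment effect, so a pre-randomisation image will not serve, and that the imaging protocol does not already settle the matter. If it does, the measurement part reduces to a missing cross-reference, and the question of population remains unless it too is dealt with there. The change should be made, but the trial's main conclusion does not depend on it.

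**What to change.** First check whether the imaging protocol or the full statistical analysis plan already defines pre-procedure patency. Then state the following in sections 6, 9.1 and 11.2, with a cross-reference to the imaging protocol:

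- **Source.** For every patient taken to angiography for possible intra-arterial intervention, in either group, the first diagnostic run, before any device or drug is used, is sent to the Trial Coordinating Centre.
- **Reading.** The existing central readers score it for patency, blinded to allocation, on a named scale with a stated cut-off if it is dichotomised.
- **Missing runs.** Give a rule for absent or unreadable runs, and report their number by group.
- **Population.** Amend section 11.2 to count patients taken to angiography but not treated because the artery was already open.
- **Limitation.** Say that selection remains. Who goes to angiography is decided after randomisation and may itself depend on response to the drug, so the comparison is not fully protected by randomisation.

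The cost is small. Assuming the run is recorded in routine care, no patient undergoes an extra procedure and no treatment rule changes. The work is a short amendment, image transfer, extra reading time and retrieval for patients already enrolled, with a few runs probably lost. Section 14 has inclusion running to September 2021, about a year after the current version (200917), so part of the collection could be prospective.

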## **12. Trial conduct and practices/procedures**

### **12.1 Compliance with regulations and guidelines**

The trial will conform to the EU Clinical Trials Directive (2001/20/EC) and national applicable regulatory requirements. EudraCT number: 2014-000096-80. ISRCTN number: 10601890. ClinicalTrials.gov number: NCT03181360.

### **12.2 Data protection**

Personal identifiers will not be stored together with clinical information about the patient, but will be stored on a separate, password-protected computer with access only for persons in the Trial Coordinating Centre who are responsible for central follow-up. The code linking personal identifiers with clinical data will be destroyed 15 years after the publication of the primary report, of the trial. The procedures for protection of personal information will be approved by the Research Ethics Committee, and data protection officials at the University Hospital of North Norway.

### **12.3 Ethical conduct**

The trial will be conducted in accordance with the MRC Guidelines for Good Clinical Practice in Clinical Trials, the Council of Europe's Convention on Human rights and Biomedicine (CETS No.: 164), the ICH Harmonized Tripartite Guideline for Good Clinical Practice (CPMP/ICH/135/95) and the Declaration of Helsinki (Edinburgh, October 2000).

We will seek informed consent from all patients, and approval from the ethics committees, according to local or national regulations. All patients will be monitored carefully during treatment and follow-up, and procedures for management of adverse drug reactions, unmasking of the trial treatment, and reporting of serious adverse events are given in the protocol. All events will be evaluated, and the trial will be monitored, audited, and inspected according to applicable regulatory requirements.

### **12.4 Liability**

Patients are indemnified by insurance specific for patients participating in trials of an Investigational Medicinal Product (IMP). Patients are also covered for non-negligent liability by the product indemnity provided by the supplier.

### **12.5 Recording and reporting of serious adverse events**

Serious adverse events will be recorded in the case report forms. In case of unexpected serious adverse events, the Trial Coordinating Centre should be notified immediately and within 24 hours at the latest, in accordance with the EC guidance document 2011/C 172/01 ("CT-3"). The report of the SAE must include an assessment of whether there is a reasonable possibility that the IMP caused the event.

Reports of suspected unexpected serious adverse reactions (SUSARs), with all relevant information, will be reported in an expedited manner by the Sponsor, to the competent authority, the ethics committee, and the Data Monitoring Committee, according to the EU Clinical Trials Directive (2001/20/EC) and applicable regulatory requirements. Copies of such reports will be sent to the principal investigators and the Sponsor. (Definitions of serious adverse events and SUSARs: See Appendix).

Serious adverse events that are expected will not be reported in an expedited manner by the Sponsor, for example recurrent ischaemic stroke, intracranial haemorrhage, myocardial infarction, or death. These are events that are expected, and that will be reported as end-points in the case

report forms. Expected adverse reactions listed in Section 4.8 of the Summary of Product Characteristics will also not be reported in an expedited manner.

## **12.6 Event adjudication**

A central Event Adjudication Committee will evaluate all events, blinded to treatment allocation.

## **12.7 Monitoring of data quality**

The central computer randomisation system will check eligibility for all patients entered in the trial. Data entered over the Internet (at trial entry) and data in case report forms will be checked for validity and internal consistency, to ensure high data quality and completeness, and coherence with the protocol. Centres with poor standards will be contacted and appropriate measures will be taken. During the course of the study the Sponsor will visit all centres at start-up and least once for monitoring purposes, with review of the CRF, comparison with source documents, and observation of the conduct of the trial and adherence to the Protocol. It will be particularly important to check that each patient exists, that a valid consent form is present in the hospital notes, to confirm patient information and adherence to the protocol. There will also be frequent telephone contacts, with the purpose of facilitating the work and fulfilling the objectives of the study.

## **12.8 Handling of protocol violations and protocol amendments**

The nature and reasons for the protocol violation shall be recorded in the CRF, in the source documents and in the monitoring visit report. All of this serious non-compliance will be followed up and reported to RA and IEC as per local regulations. In parallel, corrective and/or preventive actions will be undertaken and documented, including any retraining of the investigator and site staff. All patients who have been included in the trial will be followed up, irrespective of whether treatment was discontinued prematurely, or whether the protocol was violated. If treatment discontinuations or protocol violations become frequent the Data Monitoring Committee will consider whether there is a need to increase the number of patients to be included in the trial.

All important changes to the trial will be specified in protocol amendments. Amendments must be approved by the Steering Committee, and the Sponsor has the responsibility to seek approval from the competent authorities the ethics committees. Completed and signed protocol amendments will be circulated to all those who were on the circulation list for the original protocol. Amendments will be listed in chapter 17.

## **12.9 Monitoring of effectiveness and safety**

During the course of the trial the Data Monitoring Committee (DMC) will every 6 months perform an unblinded review of SAEs, in all patients, and in the prespecified subgroups. The DMC will also perform an unblinded interim analysis of the primary efficacy and safety variables (functional outcome and intracranial haemorrhage) when half of the patients have been included. If, in their view, there is credible evidence of harm, or overwhelming evidence of efficacy, the committee will advise the chairman of the Steering Committee. Unless this happens, the Steering Committee will remain ignorant of the interim results.

The DMC will also be responsible for monitoring the overall conduct of the trial, and may formulate recommendations relating to the selection, recruitment, or retention of participants, or their management, or to improving their adherence to protocol-specified regimens, and the procedures for data management and quality control.

The DMC will convene before the start of the trial to agree on the exact terms of reference for the committee, and will meet annually during the course of the trial.

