Based on these observations, we assume a treatment effect of 10% absolute difference in a binary endpoint setting (mRS 0-1 versus mRS 2-6) and a distribution between modified Rankin Scale categories similar to that of WAKE-UP with 42% with favourable outcome in the non-thrombolysed group vs 52% in the thrombolysed group, which corresponds to an odds ratio of 1.50. We assume a mRS distribution in the control group in six levels (categories 5 and 6 merged) as 15%, 27%, 23%, 17%, 13%, 5%, (similar to the control group the WAKE-UP trial). With a power of 80%, a two-sided significance level of 5%, and an effect size specified as an odds ratio of 1.50 from an ordinal logistic regression model, the estimated sample size is 600. Based on this, the revised target is to recruit 600 patients, i.e. 300 patients in each arm.

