## **14. Time table and end of trial**

First patient included: July 2017

Last patient included: September 2021

End of follow-up: December 2021

Presentation of main results: 2022

Follow-up by record linkage with central registries: December 2025

The end of the trial is defined as the last visit of the last patient included.

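### Does the half-way efficacy look in Protocol section 12.9, which has no numerical boundary, put the trial's error control or its revised target of 600 in doubt?

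*Protocol*

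**What the plan says.** Protocol section 12.9 has the DMC carry out an unblinded interim analysis of functional outcome and intracranial haemorrhage "when half of the patients have been included". The action is advisory: on convincing signs of harm, "or overwhelming evidence of efficacy, the committee will advise the chairman of the Steering Committee". Otherwise "the Steering Committee will remain ignorant of the interim results". Before the trial starts the DMC is to meet and "agree on the exact terms of reference for the committee".

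Section 11.2 states: "A detailed Statistical Analysis Plan has been drawn up and will be published before breaking the randomisation code". It sets a two-sided 5% level for all analyses and does not mention the interim look.

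Section 11.1 gives the current size: "the revised target is to recruit 600 patients". The version dated 180704 (Combined protocol and SAP, sections 2 and 11.1) had a target of 500, and its section 12.9 describes the look in the same terms. Section 17.7 of the Protocol lists the revised sample size under version 200917. On changes of this kind, section 12.8 says: "Amendments must be approved by the Steering Committee". Section 14 gives the recruitment window: "First patient included: July 2017", with the last inclusion in September 2021.

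**The concern.** An unblinded look at the primary outcome that can end a trial for efficacy uses some of the type I error. The protocol keeps the full 5% for its analyses and puts no figure on the evidence needed at the look. A lenient threshold would inflate the error: stopping at interim p<0.05 would take it to about 8.3%.

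Two details add to the unease. Half is counted at inclusion, while the outcome is read at 90 days, so the look would rest on fewer outcomes than its name suggests. And the target rose late in recruitment. If the look came first, a reader will ask whether anyone who knew the interim result helped to choose 600. At stake would be the validity of the final p-value and the credibility of the sample size revision in an open-label trial.

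**Working it through.** **1. The plan's own sample size.** Inputs from section 11.1: control distribution 15%, 27%, 23%, 17%, 13%, 5%; common odds ratio (OR) 1.50; power 80%; two-sided 5%. The proportional-odds formula is

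N = 12(z₀.₉₇₅ + z₀.₈₀)² / [(ln OR)²(1 − Σp̄³)],

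where p̄ is the mean of the two arms' category probabilities. Here Σp̄³ = 0.0465, so N = 12 × (1.960 + 0.842)² / (0.1644 × 0.9535) = 601. The stated 600 is reproduced. It comes from printed inputs that section 11.1 attributes to external studies, and no interim figure enters.

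**2. Type I error with the look.** Assumptions: one look at n outcomes, information fraction t = n/600, correlation √t between the interim and final statistics, final test at 1.96. Then

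error = 1 − P(|Z₁| < c₁, |Z₂| < 1.96).

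The documents give no c₁. I take p<0.001 (c₁ = 3.29) to p<0.005 (c₁ = 2.81) as the range for overwhelming evidence, and show a looser value for comparison.

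| Outcomes at the look | p<0.001 | p<0.005 | p<0.01 |
|---|---|---|---|
| 300 | 5.02% | 5.19% | 5.46% |
| 265 | 5.03% | 5.22% | 5.52% |
| 250 | 5.03% | 5.24% | 5.55% |

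The formula treats a crossed threshold as a stop, although the DMC only advises.

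**3. Power and the chance of crossing at OR 1.50.** Information is n(1 − Σp̄³)/12. With 265 outcomes the chance of meeting the criterion is 7.6% at p<0.001 and 17.2% at p<0.005; with 300 it is 9.5% and 20.4%. Overall power is 80.0% to 80.1% in all four cases.

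**4. Counting by inclusion.** From July 2017 to September 2021 is 51.0 months. If recruitment is even, that is 600/51.0 = 11.8 a month, so about 35 patients lack a 90-day outcome when patient 300 enters, which leaves about 265. In the table, moving from 300 to 265 outcomes changes the error by 0.01 to 0.03 percentage points.

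**5. Order of the look and the revision.** I read version 200917 as 17 September 2020, month 38.6. Section 14 gives only a start and an end date, so the answer depends on an assumed accrual curve.
- Even accrual: 11.8 × 38.6 gives about 454 patients in. Patient 250 enters at about month 21 and patient 300 at about month 25.5, roughly 17 and 13 months before the revision.
- Accelerating accrual, with the cumulative number growing as time squared: 600 × (38.6/51.0)² gives about 344 in. Patient 250 enters at 51.0 × √(250/600) = month 32.9 and patient 300 at 51.0 × √(300/600) = month 36.1. Adding 90 days, 300 outcomes are available at about month 39, just after the revision.

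The second curve is plausible. The Protocol summary lists Latvia, Switzerland and New Zealand, which the 180704 version does not, and the planned last inclusion moved from July 2019 to September 2021. The order is therefore open.

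**6. Worst case for the target.** Suppose the choice between 500 and 600 had been made to maximise the chance of rejection given the interim statistic z. Then

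error = ∫ φ(z) max[CP₅₀₀(z), CP₆₀₀(z)] dz,

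where CP is the conditional probability of a two-sided rejection at 1.96 under the null. The result is 5.39% for a look at 250 and 5.47% for a look at 300; adding a stop at p<0.001 gives 5.41% and 5.48%.

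**The case for a change.** The best case for a change is that the text leaves the threshold to the DMC's judgement, and looser readings cost more: 5.46% at p<0.01 and 8.31% at p<0.05, both with 300 outcomes. The reassurance on the target is also incomplete. The Steering Committee is kept from the results only unless the DMC advises it, and nothing states that this held when 600 was adopted. Section 12.8 also lets the DMC, which sees unblinded data, consider a larger trial if violations or discontinuations become frequent. One sentence would close each question.

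The textual observations stand: there is no number, no named home for one, and no statement on sequence. The consequence drawn from them does not. A 5% threshold cannot be squared with a criterion of overwhelming evidence, so 8.3% does not describe this plan. The DMC terms of reference and the SAP are the usual places for an interim rule; both are mentioned, and neither is among the documents here, so the absence of a rule cannot be inferred. No text suggests that the section 12.8 route was used, and section 11.1 gives other reasons: the ordinal primary analysis and recent wake-up stroke studies. When the look took place, and on how many outcomes, is a matter for DMC records and the trial report rather than for a plan.

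**Conclusion.** No change to the plan is needed. Section 12.9 leaves a detail unstated that a competent DMC settles in its terms of reference, and a stringent threshold of the kind the wording implies adds 0.02 to 0.24 percentage points to the 5% error, with power unchanged. Timing by inclusion is an ordinary operational trigger and makes almost no difference. The revised target rests on external evidence and reproduces from its printed inputs. Amendments pass through a committee that is not shown interim results unless the DMC raises an alarm, and even the extreme case of a fully informed choice stays below 5.5%.

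This rests on two assumptions: that overwhelming evidence means roughly p<0.005 or stricter, and that the final test is at two-sided 5%. It does not depend on whether the look came before or after version 200917, which the documents cannot settle. Naming the document that holds the interim rule, and noting that 600 was set without interim knowledge if that is so, would be a courtesy to readers. Neither would alter the analysis, the sample size or the conclusion.
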